4.0 Study Objectives

4.1 Primary Objective

The primary objective is to compare the effectiveness based on the achievement of MDA at Week 16 between subjects who had adalimumab introduced and those that had MTX escalated to the highest recommended dose of 20-25 mg ew or highest tolerable dose up to 25 mg ew after inadequate disease control on the initial MTX therapy.

4.2 Secondary Objectives

The secondary objectives are:

- To compare the effectiveness at Week 16 between subjects who had adalimumab introduced and those that had MTX escalated to the highest recommended dose of 20-25 mg ew or highest tolerable up to 25 mg ew based on the following clinical, functional and quality of life measures:
 - Psoriatic Arthritis Disease Activity Score (PASDAS)
 - Disease Activity in Psoriatic Arthritis (DAPSA) score

- Psoriatic Arthritis Impact of Disease (PsAID) score
- American College of Rheumatology criteria (ACR)
- Disease Activity Score 28 (DAS28)
- Psoriasis Area and Severity Index (PASI)
- Health Assessment Questionnaire Disability Index (HAQ-DI)
- Short Form Health Survey 36 (SF-36) scores: total, physical component summary (PCS) and mental component summary (MCS)
- Dermatology Life Quality Index (DLQI)
- Leeds Enthesitis Index (LEI)
- Tender dactylitic digit count
- To evaluate the achievement of MDA at Week 32 on each of the four different treatment regimens involving adalimumab and/or MTX in Part 2 of the study.

The study also has the following **Exploratory Objectives**:

- To evaluate the effectiveness at Week 32 based on the clinical, functional and quality of life measures described under the secondary objectives on each of the four different treatment regimens involving adalimumab and/or MTX in the second part of the study.
- To evaluate ultrasound detected synovitis and enthesitis at joint and enthesitis level, and treatment effect on each of the study treatment regimens.
- To assess the pharmacokinetic and immunogenicity of adalimumab with and without concomitant MTX.
- To investigate various biomarkers and their associations with treatment responses and outcomes.

5.0 Investigational Plan

5.1 Overall Study Design and Plan: Description

This interventional Phase 4 open-label, randomized, controlled, parallel-group, multicenter study will be conducted in two (2) parts, each of 16-week duration.

Part 1 (Day 1-Week 16) is designed to compare the achievement of MDA on adalimumab introduced in combination with MTX versus MTX alone escalated to the highest recommended dose of 20-25 mg ew^{11,27} or highest tolerable dose up to 25 mg ew, whatever feasible, in PsA subjects inadequately controlled after the initial course of MTX at 15 mg ew. Part 1 will be open-label, randomized, controlled, parallel group.

Part 2 (Week 16-32) is to evaluate the effectiveness of four (4) different treatment regimens consisting of adalimumab and/or MTX in maintaining or attaining MDA, as applicable. Part 2 will be open-label, parallel group. Subjects will be assigned into the four treatment arms based on their MDA status at Week 16 and initial randomized treatment. Starting at Week 24, there will be rescue treatment option based on not achieving MDA and investigator's judgment.

Eligible male and female subjects with PsA will be selected to participate in the study according to the selection criteria.

The study will enroll approximately 240 subjects at approximately 60 sites to meet the scientific and regulatory objectives without enrolling an undue number of subjects in alignment with ethical considerations. Therefore, if the target number of subjects has been enrolled, there is a possibility that additional subjects in screening will not be enrolled.

Following a screening period of up to 30 days, subjects meeting the selection criteria will be randomized in a 1:1 ratio to either of the two (2) arms and treated for 16 weeks in Part 1:

- Arm 1/Part 1: Adalimumab 40 mg eow in combination with MTX 15 mg ew (ADA 40 mg eow + MTX 15 mg ew),
- Arm 2/Part 1: MTX escalated to 20-25 mg or highest tolerable dose ew (MTX 20-25 mg or highest tolerable dose ew).*

* MTX will be escalated by increments of 5.0 mg every 2 weeks, starting at 20 mg ew as the first MTX dose on or after Day 1, depending on the subject's MTX administration schedule prior to the study. In the case of

suspected MTX intolerance or toxicity, the MTX dose may be de-escalated by 5 mg and the subject may stay on the highest tolerable MTX dose below 20-25 mg ew as described per the protocol (see Section 6.1.7, Toxicity Management). The event of MTX toxicity or intolerance must be clearly documented in source documents. MTX dose should not exceed 25 mg ew in this study.

After the assessment of MDA at Week 16 (primary endpoint), subjects will be assigned to one of the four (4) treatment arms based on the achievement of MDA and initial randomized treatment, and treated for additional 16 weeks in Part 2 as follows:

[figure not shown]
- Arm 1/Part 2: Subjects achieving MDA at Week 16 on adalimumab 40 mg eow plus MTX 15 mg ew, will have MTX completely withdrawn at Week 16 and continue receiving adalimumab as monotherapy (ADA 40 mg eow),
- Arm 2/Part 2: Subjects not achieving MDA at Week 16 on adalimumab 40 mg eow plus MTX 15 mg ew, will have adalimumab escalated to 40 mg ew in combination with MTX 15 mg ew (ADA 40 mg ew plus MTX 15 mg ew),
- Arm 3/Part 2: Subjects achieving MDA at Week 16 on MTX escalated to 20-25 mg or highest tolerable dose ew, will continue with the same MTX dose (MTX 20-25 mg or highest tolerable dose ew),
- Arm 4/Part 2: Subjects not achieving MDA at Week 16 on MTX escalated to 20-25 mg or highest tolerable dose ew, will receive adalimumab 40 mg eow in combination with MTX 20-25 mg or highest tolerable dose ew (ADA 40 mg eow plus MTX 20-25 mg or highest tolerable dose ew).

Subjects in Arms 1-4 of Part 2 of the study will have the option of being rescued, starting at Week 24 and based on the subject not achieving MDA and the Investigator's judgment. The selection of the rescue treatment regimen will be at the discretion of the Investigator, but should involve adalimumab and/or MTX and should not involve prohibited medications per the protocol. The recommended rescue treatment regimens are as follows:

- Subjects not achieving MDA on adalimumab 40 mg eow (Arm 1) have MTX 15 mg ew added,
- Subjects not achieving MDA on adalimumab 40 mg ew + MTX 15 mg ew (Arm 2) have MTX escalated to 20-25 mg ew,
- Subjects not achieving MDA on MTX 20-25 mg or highest tolerable dose ew (Arm 3) have adalimumab 40 mg eow added,
- Subjects not achieving MDA on adalimumab 40 mg eow + MTX 20-25 mg or highest tolerable dose ew (Arm 4) have adalimumab escalated to 40 mg ew.

A schematic of the study design is shown below in [Figure 1](#):

Figure 1. Control Design Scheme

Both adalimumab and MTX will be provided as study drugs.

MTX will be provided as a study drug for either oral or subcutaneous (sc) administration. The route of MTX administration can be selected at the discretion of the Investigator and may be exchanged between oral and sc at any time during the study.

5.1.1 Screening Period

At the Screening Visit, subjects who provide written (signed and dated) informed consent prior to any study specific procedures, will receive a unique subject number via Interactive Response Technology (IRT) system and will undergo the study procedures identified in Section 5.3.1.1 associated with the Screening Visit. The investigator will evaluate whether the subject meets all of the eligibility criteria specified in Section 5.2.1 and Section 5.2.2 during the period from the Screening Visit through Day 1 prior to dosing and record the results of this assessment and the details of the informed consent process in the subject's medical records. Eligible subjects have up to 30 days following the Screening Visit to enroll into the study. The screening period may be extended with the approval of the AbbVie TA MD for certain circumstances (e.g., due to delay of availability of screening test results, holidays or scheduling/availability issues).

5.1.1.1 Rescreening

- Subjects that initially screen fail for the study may be permitted to re-screen once. There is no minimum period of time a subject must wait to re-screen for the study. All screening procedures with the possible exceptions noted below will be repeated.
- Re-consent is required if there is a newly approved informed consent since the original screening visit or if 60 days have passed.
- If there is one exclusionary laboratory result during screening, a re-test of that one particular value is allowed without repeating all other laboratory tests provided no more than 30 days have passed since the original screening visit.
- If the subject had a complete initial Screening visit including the assessment of a PPD test (or equivalent), or QuantiFERON-TB Gold test, Chest x-ray (if applicable) and ECG, these tests will not be required to be repeated for the re-screening visit, provided the conditions noted in Section 5.2 are met and no

more than 90 days have passed since the original screening visit. Note: If the subject initiated TB treatment and the treatment was completed outside the 30 day screening window, the screening period may be extended with the approval of the AbbVie TA MD.

The subject must meet all inclusion and none of the exclusion criteria at the time of enrollment in order to qualify for the study. As appropriate, sites are encouraged to contact the AbbVie Therapeutic Area Medical Director (TA MD) to confirm if subjects should or should not be re-screened.

For subjects who do not meet the study eligibility criteria, the site personnel must register the subject as a screen failure in both IRT and electronic data capture (EDC) systems. For subjects that re-screen, the Screening number assigned by the IRT at the initial Screening visit should be used; a new Screening number should not be requested.

5.1.2 Treatment Period

5.1.2.1 Part 1 (Randomized Open Label Treatment Period)

At the Baseline visit, subjects who meet all the inclusion criteria and none of the exclusion criteria described in Section 5.2.1 and Section 5.2.2 will be enrolled into the study and randomized in a 1:1 ratio to Arm 1 or Arm 2 of Part 1 (as described in Section 5.1). During this period of the study, subjects will visit the study site at Week 2, Week 4 and then monthly through Week 16 (if local requirements ask for additional safety assessments, e.g., due to MTX treatment, respective laboratory tests should be done locally). A \pm 2-day window is permitted around scheduled study visits.

IRT will be utilized to dispense the appropriate study drug (adalimumab and MTX) to subjects for administration during the visit or at the regularly scheduled day for MTX. Subjects will be given dosing instructions and a dosing diary at the Baseline visit.

5.1.2.2 Part 2 (Open-Label Treatment Period)

After completing the randomized-open label treatment period at Week 16, subjects will be assigned to Arms 1-4 of Part 2 (as described in Section 5.1), based on the achievement of MDA and initial randomized treatment, and treated for additional 16 weeks. Starting at Week 24, there will be rescue treatment option based on not achieving MDA and investigator's judgment. During this study period, subjects will visit the study site monthly through Week 32. A \pm 2-day window is permitted around scheduled study visits. Subjects will be dispensed study drugs at the Week 16 Visit for administration during the visit or at the regularly scheduled day for MTX.

No study drug will be administered or injected after the final visit (Week 32 Visit). Subjects may discontinue study drug treatment at any time during study participation. Subjects who end study participation early will have a Premature Discontinuation (PD) Visit and complete the procedures outlined for the PD Visit in Appendix C as soon as possible after the last dose of study drug and preferably prior to the administration of any new therapies.

Follow-Up Period

Subjects may discontinue their study participation at any time. Subjects that end study participation early will have a PD Visit. All subjects will have a follow-up phone call 70 days (\pm a 7 day window) after the last administration of adalimumab to obtain information on any new or ongoing AEs. For subjects taking only MTX, the follow-up phone call will occur 70 days (\pm 7 day window) after the last administration of MTX.

5.2 Selection of Study Population

Approximately 240 adult subjects with active PsA (defined as not in MDA and having at least 3 tender and 3 swollen joints) despite having been treated with the first course of MTX at the dose of 15 mg ew for \geq 4 weeks and biologic naive who meet all the inclusion and none of the exclusion criteria are planned to be enrolled in the study at approximately 60 sites.

5.2.1 Inclusion Criteria

1. Adult male or female, ≥ 18 years of age at Screening.
2. PsA diagnosis established at least 4 weeks prior to the date of the Screening visit and confirmed by CASPAR criteria at the Screening visit
3. Not in Minimal Disease Activity (MDA) at the time of screening, defined as not meeting at least 5 of the following 7 criteria:
 - Tender joint count (TJC) ≤ 1 out of 68 assessed
 - Swollen joint count (SJC) ≤ 1 out of 66 assessed
 - PASI ≤ 1 or body surface area (BSA) ≤ 3
 - Patient's assessment of pain visual analogue scale (VAS) ≤ 15
 - Patient's global assessment of disease activity (PtGA) VAS ≤ 20
 - HAQ-DI score ≤ 0.5
 - Tender enthesal points ≤ 1 out of 8 assessed
4. Has active arthritis defined as fulfilling both the below criteria at screening and baseline visits:
 - ≥ 3 tender joints (out of 68 assessed)
 - ≥ 3 swollen joints (out of 66 assessed)
5. Treated with MTX 15 mg ew for PsA defined as:
 - Oral or subcutaneous (sc) administration of MTX for at least 4 weeks prior to screening,
 - Change of the MTX administration route (oral or sc) is permitted in this time period if the administered dose of MTX 15 mg ew is not changed,
 - This is the first course of MTX the subject has been receiving for the treatment of PsA,
 - Subject has not received a dosage of MTX higher than 15 mg ew prior to the screening visit,
 - Subject could have been receiving MTX doses lower than 15 mg ew before reaching the stable dose of MTX 15 mg ew defined above,

- If the subject had been on MTX 15 mg ew for ≥ 12 weeks, temporary MTX discontinuation or dose decrease below 15 mg ew for up to 4 weeks is allowed.
6. If subject is receiving concomitant oral corticosteroids, prednisone or equivalent must be ≤ 10 mg/day and the dose must be stable for at least 1 week prior to the Baseline visit
 7. If subject is receiving nonsteroidal anti-inflammatory drugs (NSAIDs), including cyclooxygenase (COX) 2 selective inhibitors, paracetamol (up to the maximum recommended dose in the local country label), the dose must be stable for at least 1 week prior to the Baseline Visit
 8. If subject is receiving other csDMARDs in addition to MTX (i.e., sulfasalazine), the dose must be stable for at least 4 weeks prior to the Baseline visit. If csDMARDs are discontinued before study enrollment, the discontinuation must occur at least 4 weeks prior to the Baseline Visit
 - Leflunomide should be discontinued at least 4 weeks prior to the Baseline visit
 9. Subject must be able and willing to self-administer sc injections or have a qualified person available to administer sc injections
 10. Laboratory values of the following at the Screening visit:
 - Hemoglobin count > 8.5 g/dL
 - White blood count (WBC) $> 3.5 \times 10^9/L$
 - Platelet count $> 100 \times 10^9/L$
 - Absolute neutrophil count (ANC) $> 1.5 \times 10^9/L$
 - Alanine aminotransferase (ALT) and aspartate aminotransferase (AST) levels must be within 3 times the upper limit of normal range (ULN) for the laboratory conducting the test
 11. Subject has a negative TB Screening Assessment. If the subject has a positive TB test or evidence of a latent TB infection, the subject must initiate and complete a minimum of 2 weeks (or per local guidelines, whichever is longer) of an ongoing

TB prophylaxis or have documented completion of a full course of TB prophylaxis, prior to Baseline. (See Section 5.3.1.1)

12. Subject is judged to be in good health as determined by the Investigator based upon the results of medical history, laboratory profile, physical examination, chest x-ray (CXR), and a 12-lead electrocardiogram (ECG)
13. A negative serum pregnancy test at the Screening visit and a negative urine pregnancy test for women of childbearing potential at the Baseline visit (prior to administration of first dose of study drug). A serum pregnancy test will also be taken at the Baseline visit if the urine pregnancy test is positive. If the serum result at the Baseline visit is positive, the subject will be discontinued from the study
14. If female subject, is either not of childbearing potential (defined as postmenopausal for at least 1 year prior to Screening), or surgically sterile (bilateral salpingectomy, bilateral oophorectomy and/or hysterectomy), or is of childbearing potential and is practicing an approved method of birth control (refer to Section 5.2.4) throughout the study and for 180 days after last dose of study drug.
15. Male subjects who are sexually active with female partner(s) of childbearing potential, must agree, from Study Day 1 through 180 days after the last dose of study drug to practice the protocol specified contraception (Section 5.2.4).
A condom without spermicide is acceptable in countries where spermicide is not available
16. Subjects must voluntarily sign and date an informed consent, approved by an Independent Ethics Committee (IEC)/Institutional Review Board (IRB), prior to the initiation of any screening or study-specific procedures

Rationale for the Inclusion Criteria:

- | | |
|---------|--|
| 1 – 9 | To select the adequate subject population for this study |
| 10 – 12 | For the safety of the study subjects |

- 13 – 15 The impact of adalimumab on pregnancies is unknown. MTX is teratogenic and may be genotoxic
- 16 In accordance with harmonized GCP

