5.2.4 Contraception Recommendations and Pregnancy Testing

Contraception Recommendation for Females

If female, subject must be either permanently surgically sterile (bilateral oophorectomy, bilateral salpingectomy or hysterectomy) or postmenopausal defined as:

- Age > 55 years with no menses for 12 or more months without an alternative medical cause.
- Age < 55 years with no menses for 12 or more months without an alternative medical cause AND an FSH level > 40 IU/L.

A woman who does not meet the definition of postmenopausal or permanently surgically sterile is considered of childbearing potential and is required to practice at least one of the following methods of birth control, on Study Day 1 (or earlier) through at least 180 days after the last dose of study drug.

- Combined (estrogen and progestogen containing) hormonal contraception (oral, intravaginal, transdermal) associated with the inhibition of ovulation, initiated at least 90 days prior to Study Day 1.
- Progestogen-only hormonal contraception (oral, injectable, implantable) associated with inhibition of ovulation, excluding low-dose oral gestagens (mini-pills containing either lynestrenol or norethisteron) initiated at least 90 days prior to Study Day 1.
- Bilateral tubal occlusion/ligation.
- Bilateral tubal occlusion via hysteroscopy (i.e, Essure), provided a hysterosalpingogram confirms success of the procedure.
- Vasectomized partner(s), provided the vasectomized partner has received medical assessment of the surgical success and is the sole sexual partner of the women of childbearing potential study participant.
- Intrauterine device (IUD).
- Intrauterine hormone-releasing system (IUS).

- True abstinence: Refraining from heterosexual intercourse when this is in line with the preferred and usual lifestyle of the subject (periodic abstinence [e.g., calendar, ovulation, symptothermal, post-ovulation methods] and withdrawal are not acceptable).

If required per local practices, male or female condom with or without spermicide OR cap, diaphragm or sponge with spermicide should be used in addition to one of the birth control methods listed above (excluding true abstinence).

Contraception Recommendation for Males

If the male subject has a female partner who is postmenopausal or permanently sterile (bilateral oophorectomy, bilateral salpingectomy or hysterectomy), no contraception is required.

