All subjects will be tested for the presence of the Hepatitis B Virus (HBV) at Screening. A positive result for the Hepatitis B surface antigen (HBs Ag) will be exclusionary. Samples that are negative for HBs Ag will be tested for surface antibodies (HBs Ab) and core antibodies HBc Ab Total). Subjects with HBs Ag (-), HBs Ab (-), and HBc Ab Total (+) require PCR qualitative testing for HBV DNA. Any HBV DNA PCR result that meets or exceeds detection sensitivity will be exclusionary.

Subjects with a negative HBs Ag test and tests showing the results below, do not require HBV DNA PCR qualitative testing.

- HBc Ab Total (-) and HBs Ab (-)
- HBc Ab Total (-) and HBs Ab (+)
- HBc Ab Total (+) and HBs Ab (+)

Hepatitis C Testing:

Blood samples for Hepatitis C serology will be obtained at the Screening Visit. A subject will not be eligible for study participation if test results indicate active Hepatitis C (HCV RNA detectable in any subject with anti HCV Ab).

Pregnancy Test

A serum pregnancy test will be performed at the Screening Visit on all female subjects of childbearing potential. At the Baseline Visit, subjects of childbearing potential will have a urine pregnancy test performed locally by designated study personnel. A serum

pregnancy test will also be taken on Day 1 if the urine pregnancy test is positive. If the serum result at Day 1 is positive, the subject is considered a screen failure. Investigators may conduct more frequent urine pregnancy testing as necessary according to their judgment. If any urine pregnancy test is positive, a serum pregnancy test will be performed by the central laboratory. A lactating or pregnant female will not be eligible for participation or continuation in this study.

Starting at baseline, all women of childbearing potential will have a urine pregnancy test performed locally by designated study personnel at each visit, including at the last dose and PD visit, if applicable (see [Appendix C](#)).

Clinical Laboratory Tests

Blood and urine samples will be obtained for clinical laboratory tests. Samples will be obtained at the designated study visits as specified in [Appendix C](#). Samples will be obtained for the laboratory tests listed in [Table 1](#).

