Table 1. Clinical Laboratory Tests

Hematology	Clinical Chemistry	Urinalysis	Other Laboratory Tests
Hematocrit	Blood Urea Nitrogen (BUN)	Specific gravity	Serum pregnancy test
Hemoglobin	Creatinine	Ketones	Urine pregnancy test
Red Blood Cell (RBC) count	Total bilirubin	pH	HIV, if applicable (testing to be conducted at local lab)
White Blood Cell (WBC) count	Albumin	Protein	HBsAg
Neutrophils	Aspartate aminotransferase (AST)	Glucose	HBsAb
Bands	Alanine aminotransferase (ALT)	Blood	HBcAb
Lymphocytes	Alkaline phosphatase	Leukocytes	HBV PCR
Monocytes	Sodium	Nitrites	HCV PCR
Basophils	Potassium		PPD or the QuantiFERON-TB Gold test
Eosinophils	Chloride		hs-CRP
Platelet count (estimate not acceptable)	Calcium		FSH*
	Inorganic phosphorus		
	Uric acid		
	Cholesterol		
	Total protein		
	Glucose		
	Triglycerides		
	Sodium bicarbonate		

* If applicable.

Assessment of Peripheral Joints

Tender Joint Count (TJC) and Swollen Joint Count

(SJC)

TJC68 and SJC66, including the DIP joints of the hands and excluding hips for swelling, will be performed as recommended for clinical trials in PsA.⁴¹ Additionally, the TJC28 and SJC28 required for the calculation of DAS28 will be extracted from the corresponding TJC68 and SJC66, respectively. The TJC/SJC assessments will be performed at the visits specified in [Appendix C](#).

Tender Joint Count (TJC)

An assessment of 68 joints (TJC68; [Appendix E](#)) will be done for tenderness by pressure manipulation on physical examination. Joint pain/tenderness will be classified as either present ("1"), absent ("0"), replaced ("9") or no assessment ("NA").

Swollen Joint Count (SJC)

An assessment of 66 joints (SJC66; [Appendix E](#)) will be done by physical examination. The joints to be examined for swelling are the same as those examined for tenderness, except the hip joints excluded. Joint swelling will be classified as present ("1"), absent ("0"), replaced ("9") or no assessment ("NA").

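### Inclusion 14 defines non-childbearing status more loosely than Section 5.2.4, so a site using it alone could leave a woman under 55 on methotrexate without contraception or scheduled pregnancy tests

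*Protocol*

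**What the plan says.** Inclusion 14 in Protocol Section 5.2.1 accepts a female subject who "is either not of childbearing potential (defined as postmenopausal for at least 1 year prior to Screening", or who is surgically sterile, or who "is of childbearing potential and is practicing an approved method of birth control (refer to Section 5.2.4) throughout the study"; the birth-control requirement extends to 180 days beyond the final dose. The only pointer to Section 5.2.4 is in that last branch and concerns the birth-control method.

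Section 5.2.4 has its own definition of postmenopausal, in two age bands. Over 55, it needs 12 months or more without menses and no other medical explanation. The younger band reads "Age < 55 years with no menses for 12 or more months without an alternative medical cause AND an FSH level > 40 IU/L". The section then sets a default: "A woman who does not meet the definition of postmenopausal or permanently surgically sterile is considered of childbearing potential and is required to practice" contraception, using one or more of the listed methods.

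Pregnancy testing follows the same classification. Section 5.3.1.1 states "A serum pregnancy test will be performed at the Screening Visit on all female subjects of childbearing potential", and it adds for later visits: "Starting at baseline, all women of childbearing potential will have a urine pregnancy test performed locally by designated study personnel at each visit". Inclusion 13 asks for "A negative serum pregnancy test at the Screening visit and a negative urine pregnancy test for women of childbearing potential at the Baseline visit".

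FSH appears in Table 1 with a footnote that makes it conditional. Appendix C has no FSH row.

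**The concern.** The protocol has two definitions of the same status, and they disagree for an identifiable group: mainly women under 55, not surgically sterile, without menses for a year and regarded as menopausal, whose FSH is 40 IU/L or lower or was never measured. By requiring FSH in Section 5.2.4, the sponsor itself treats a year of amenorrhoea as insufficient proof in this age group. The looser wording sits in the eligibility list.

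Childbearing status decides who must use contraception and who is tested for pregnancy at each visit. The rationale under the inclusion criteria describes methotrexate as teratogenic and possibly genotoxic. Both randomized arms take it in Part 1, and one arm escalates the dose. A wrong classification at Screening would remove both routine safeguards for the rest of the study.

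**Working it through.** The protocol gives no figure to reproduce here. The check sets the two definitions side by side and then counts what depends on them.

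| | Inclusion 14 | Section 5.2.4 |
|---|---|---|
| Duration | Postmenopausal for 1 year or more | 12 months or more without menses |
| Other causes of amenorrhoea ruled out | Not stated | Required |
| FSH, under 55 | Not stated | Above 40 IU/L |
| Women not meeting the definition and not surgically sterile | No default stated | Of childbearing potential |

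**Worked case.** Take a woman aged 50, not surgically sterile, 14 months without menses, no FSH result.

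- A site that accepts her as postmenopausal under inclusion 14 classes her as not of childbearing potential. She then has no contraception requirement and no scheduled urine tests.
- Under Section 5.2.4 she is of childbearing potential. She then needs contraception until 180 days after the last dose, a serum test at Screening, and urine tests from Baseline.

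**Could a site use inclusion 14 alone?** Sections 5.1.1, 5.1.2.1 and 5.5.3 send the eligibility decision to Sections 5.2.1 and 5.2.2, and none names 5.2.4. About 60 sites will apply the criteria.

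**Does the schedule prompt the FSH test?** No. HIV testing makes a useful comparison. Table 1 marks it "if applicable" too, yet Appendix C gives HIV a Screening entry and a footnote saying when to test. FSH has neither.

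**Would deviation reporting catch it?** Not reliably. Section 7.0 lists failed entry criteria, missed withdrawals, wrong treatment or dose, and prohibited treatment. A woman who passes inclusion 14 as worded has not failed that criterion, and absent contraception is not a listed category.

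**Scheduled tests for one woman completing Week 32 (Appendix C).**

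- Urine tests: Day 1 and Weeks 2, 4, 8, 12, 16, 20, 24, 28 and 32 = 10.
- Serum test at Screening = 1, lost only if Section 5.3.1.1 and Appendix C footnote k govern. They limit it to women of childbearing potential, whereas inclusion 13 can be read as requiring it without that limit.
- Total: 10 or 11.

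**Contraception period for a completer, Day 1 to 180 days after the last dose (visit windows ignored).**

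- Last every-other-week adalimumab dose at Week 30: 30 × 7 + 180 = 390 days.
- Last weekly dose at Week 31: 31 × 7 + 180 = 397 days.
- Ceiling, since no drug is given after the Week 32 visit: 32 × 7 + 180 = 404 days.

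The 390-day case fits only Arm 1 of Part 2 without rescue, where methotrexate stops at Week 16. Arms that continue weekly dosing fall at about 397 days or above.

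**The case against.** The strongest reply is that Section 5.2.4 is mandatory and is the only place where the protocol defines postmenopausal in terms of age and FSH. Inclusion 14 cites that section in the same sentence. Read as a whole, the protocol does not waive contraception for this woman, and a site that ignored 5.2.4 would be breaching it. This stands, and it limits the problem to sites that apply inclusion 14 on its own wording. It does not remove the conflict, because inclusion 14 offers a complete definition and cites 5.2.4 only for a woman already judged fertile.

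A second reply is that inclusion 14 says postmenopausal, not merely without menses, so amenorrhoea from another cause is arguably excluded already. The phrase could even mean a year beyond the 12 months that establish menopause, in which case the woman with 14 months would not qualify. Both readings are possible. On the longer reading, the same case arises at 12 + 12 = 24 months, still with no FSH result. FSH confirmation under 55 is the clearest remaining gap.

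A third reply is that other safeguards exist. Exclusions 30 and 31 bar women who are pregnant or planning pregnancy, investigators may test more often, pregnancy leads to withdrawal, and pregnancies are collected to 180 days after the last dose. Subjects were also already taking methotrexate 15 mg weekly before screening. All of this is true, but none of it replaces contraception or scheduled testing for a woman recorded as not fertile.

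Finally, the test and day counts describe a schedule and do not measure harm. That is correct, and nothing in the documents shows that any such woman will enrol.

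**Conclusion.** The concern holds. On its own wording, inclusion 14 can give the opposite classification to Section 5.2.4 for a woman under 55 whose menopause has not been confirmed, and that classification controls contraception and scheduled pregnancy testing during treatment with a teratogen.

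For each misclassified woman who completes the study, 10 or 11 scheduled tests and about 390 to 404 days of required contraception are at stake. The documents give no age, sex or FSH data, so the number affected cannot be estimated and may be small. The conclusion assumes that at least one site applies inclusion 14 without carrying over the Section 5.2.4 definition. The matter is one of subject safety and internal consistency, and it has no bearing on the primary analysis or sample size. It should be corrected.

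**What to change.** 1. In inclusion 14, replace the parenthesis with: *postmenopausal as defined in Section 5.2.4*.
2. Add the FSH test to the Appendix C Screening column, with a footnote limiting it to women in the FSH band of Section 5.2.4: under 55, 12 months or more without menses, and not surgically sterile.

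The cost is one phrase, one schedule row and one footnote. FSH is already in Table 1, so no new assay is needed. A few women may be asked for an FSH test, contraception and urine tests. Section 5.2.4 already implies these requirements for them.
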